1.2 Background

REN001 is a potent, selective and orally bioavailable PPAR δ agonist. PPAR δ controls genes involved in cellular metabolic processes such as glucose homeostasis, fatty acid synthesis and storage, and fatty acid mobilization and metabolism. PPAR δ is expressed in several metabolically active tissues including liver, muscle, and fat. It is the most abundant PPAR isoform in skeletal muscle and has a higher expression in oxidative type I muscle fibers compared with glycolytic type II muscle fibers. REN001 potently and selectively activates PPAR δ and increases fatty acid oxidation supporting the rationale of developing REN001 in the treatment of patients with mitochondrial myopathies.

Full details of the REN001 chemistry, pre-clinical and clinical data can be found in the current Investigator's Brochure.

1.3 Study Rationale

There is a strong rationale for the use of REN001, a selective PPAR δ agonist, in patients with PMM. The PPAR δ receptor is a nuclear receptor primarily found in skeletal muscle. Patients with PMM caused by genetic mutations in the mitochondrial or nuclear genomes have impaired oxidative phosphorylation. Selective PPAR agonists may ameliorate the cellular energy deficit in patients with these mutations by:

- Increasing fatty acid oxidation (FAO) and OXPHOS activity resulting in enhanced mitochondrial adenosine triphosphate (ATP) generating capacity.
- In mtDNA-PMM, increasing the proportion of wild-type mitochondria. Although mitochondrial disease--induced mitochondrial proliferation may favor mutated mitochondria, pharmacological upregulation of mitochondrial biosynthesis increases the number of both mutated and wild-type mitochondria, which allows wild-type mitochondria to compensate for mutant mitochondria.
- Increasing mitochondrial biogenesis and thereby increasing residual OXPHOS activity, which would enhance the cellular ATP synthesis capacity.

The information collected will support the long-term safety evaluations of REN001 in the total PMM population. Enrolment of PMM patients with nDNA mutations in the REN001-202 OLE study offers the opportunity to rapidly gain safety, tolerability and exploratory efficacy data on the effect of REN001 in these patients. The information obtained will then be used to support further clinical development of REN001 in this population.

This protocol amendment expands the duration of the study to 48 months, to enable subjects who have perceived benefit from therapy to continue to receive REN001.

1.4 Risk-Benefit Assessment

1.4.1 Benefits

In Study REN001-101, an open label Phase 1b study in subjects with mtDNA PMM, oral REN001 dosed at 100mg per day was safe and well tolerated for 12 weeks (Part A) and up to an additional 24 weeks in the subjects who continued into an extension part of the study (Part B). Following 12 weeks of dosing, most subjects experienced improvement in the outcome measures of distance walked in the 12MWT and symptoms of fatigue and pain evaluated with Patient Reported Outcome (PRO) measures. The study was terminated early in 2020 due to the operational obstacles created by the Corona Virus Disease 2019 (COVID-19) pandemic. Subjects who were ongoing in the study when Study REN001-101 was terminated will be given the opportunity for further treatment with REN001 in this study.

The STRIDE study is an ongoing double-blind, placebo-controlled, Phase 2b study to evaluate the efficacy and safety of 24 weeks treatment with REN001, dosed at 100mg per day, in mtDNA PMM subjects. This long-term safety study will offer the opportunity for extended active treatment for those subjects randomized to REN001 in STRIDE, and active treatment for subjects who were randomized to placebo. Neither subjects nor sites will be aware of the allocated treatment in STRIDE when rolling directly into this study, and the Sponsor will remain blinded to this information until the STRIDE database is locked and treatment allocation unblinded.

Patients with nDNA mutations will not have previously participated in studies in the REN001 program (due to eligibility criteria designed to maintain a homogenous population). However, the potential for REN001 to provide benefit for PMM patients is based on the myopathic phenotype, rather than specific genetic cause. Therefore, after gaining experience in the

mtDNA-PMM population, this protocol was amended (Version 2.0) to widen enrollment to include adult PMM patients with nDNA mutations. This will provide long-term safety data on the total PMM patient population and provide evidence of potential efficacy in the nDNA-PMM population.

This amendment increases the duration of the study from 24 months to 48 months. The duration of the study has been increased to continue the collection of long-term safety and also to enable access to REN001 therapy to those subjects who may be benefiting from REN001 treatment.

1.4.2 Risks

1.4.2.1 Elevated Creatine Kinase

Subjects with PMM may have asymptomatic benign raised baseline creatine kinase (CK) levels as part of the PMM disease. Even among healthy individuals CK levels rise transiently after exercise or intense physical activity. In patients with PMM, serum CK levels may increase to as much as 30 times the ULN within 24 hours after strenuous physical activity, then slowly decline over the next 7 days. The degree of CK elevation depends on the type and duration of exercise, with greater elevation in those who are untrained ([Moghadam-Kia, Oddis, & Aggarwal, 2016](#)). It is possible that improvements in the cellular energy deficit with REN001 treatment may result in increased muscle use and transient benign muscle enzyme elevations.

Serum CK data from subjects with PMM in the Phase 1b study (REN001-101) demonstrated a pattern of transient, elevated CKs following exercise and the collection of muscle biopsies; none of these elevations were associated with myoglobinuria. The elevations seen were self-limited and resolved with no intervention despite continued treatment with REN001 and continuation of the subject's normal activities of daily living, including exercise. In all clinical trials of REN001 to date, elevations in CK tended to be modest and reversible and were usually determined by investigators as unlikely to be associated with REN001 treatment. In the current study as a precautionary measure CK levels will be assessed throughout the study.

1.4.2.2 Cataract Formation

A finding of cataract was observed in a high dose 6-month rat chronic toxicology study. Importantly, no cataracts were observed in any other toxicology studies, including in a 3-month rat study and a 12-month primate study. It is predicated that the changes observed in the 6-month rat study are rat strain specific. Nevertheless, following this observation, taking a conservative approach, ophthalmology examinations are being included in all REN001 trials. Slit lamp eye examinations will be conducted together with assessments of best corrected visual acuity during this study.

1.4.2.3 Potential Drug-Drug Interactions

REN001 is not a direct or time-dependent inhibitor of CYP3A4. However, REN001 has been shown to be a weak inducer of CYP3A4 *in vitro*. A potential for drug interactions between REN001 and drugs that are metabolized through CYP3A4 is considered low but cannot yet be ruled out. Therefore, drugs that are metabolized primarily by CYP3A4 and have a narrow therapeutic index should be administered with caution in subjects participating in REN001 studies.

There are few commonly used CYP3A4 substrates with a narrow therapeutic index which are not already prohibited by the protocol ([Table 1](#)). It is standard clinical practice to evaluate every patient as an individual with their own context of comorbid conditions and concurrent

medications. In order to ensure Investigators are checking the most up-to-date references for potential drug-drug interactions, they are referred to their own national medical prescribing guidance if available and to the Flockhart Table¹ maintained by the University of Indiana available at <https://drug-interactions.medicine.iu.edu/> if they are in any doubt about the status of a proposed concomitant medication.

REN001 was identified as a P-glycoprotein (P-gp) substrate *in vitro*. Strong P-gp inhibitors may have an impact on the absorption and metabolism of a P-gp substrate, however preliminary human metabolism for REN001 indicates numerous metabolic pathways are involved in the clearance of REN001. Therefore, it is unlikely that co-administration of a strong P-gp inhibitor with REN001 will result in higher systemic exposures of REN001. Co-administration of REN001 with a strong P-gp inducer may reduce REN001 plasma concentrations.

1.4.2.4 Fertility and Contraception

In accordance with the latest European regulatory discussions and guidelines ([Clinical Trials Facilitation Group, 2014](#) and [2020](#)), WOCBP are eligible for the study provided they are using a highly effective form of contraception while taking the study drug and for approximately 30 days after stopping study drug (at least one menstrual cycle after drug exposure). If subjects are transferred to a commercial supply of REN001 they must be advised to adhere to the contraceptive requirements. Serum pregnancy testing will be completed at screening for mtDNA-PMM subjects enrolling after exiting one of the two feeder studies and for nDNA-PMM subjects. Urine pregnancy tests will be carried out at baseline and monthly thereafter until completion of the study for all WOCBP regardless of when they enrolled.

Fertile men (i.e., unless permanently sterile by bilateral orchidectomy) must use a condom during intercourse with a WOCBP from baseline through to at least 14 weeks after stopping study drug (at least one sperm cycle after drug exposure) and should not father a child in this period. A condom is also required to be used by vasectomized men to prevent delivery of the drug via seminal fluid.

As REN001 is a weak inducer of CYP3A4 *in vitro*, caution is advised when co-administering REN001 and oral contraceptive agents. As a precautionary measure, women taking highly effective hormonal contraception therapy will be advised to use an additional effective non-hormonal method of contraception during treatment with REN001 and for 30 days after the final dose of study drug ([Section 5.8](#)).

1.4.2.5 Carcinogenicity

Carcinogenicity studies have been initiated but are not yet completed. Animal carcinogenicity data in rodents suggest that some, but not all, PPAR agonists have carcinogenicity potential. The mechanism by which implicated compounds produce tumors in rodents is not well understood and the relevance of these findings for other classes of PPAR agonists, if any, to humans is unknown. Subjects with a history of cancer, except *in situ* basal cell carcinoma in the skin, are excluded from participation in the study.

¹ Flockhart DA, Thacker, D., McDonald, C., Desta, Z. *The Flockhart Cytochrome P450 Drug-Drug Interaction Table*. Division of Clinical Pharmacology, Indiana University School of Medicine (Updated 2021). <https://drug-interactions.medicine.iu.edu/>. [Accessed 23 March 2022].

1.4.2.6 Bone

A finding of premature bone plate closure was observed in toxicology studies in one species of rat. This finding was not seen in the non-human primate studies. As a precaution, treatment-naïve nDNA-PMM subjects under 25 years of age will have a wrist x-ray prior to enrolment to confirm skeletal maturity.

PPAR γ agonists have been associated with bone loss. Currently it is not known if REN001 (a selective PPAR δ agonist) will have any impact on bone mineral density (BMD). Nonetheless, given the requirements for walk tests and taking a conservative approach, the Sponsor excluded subjects with a history of fragility/stress fractures or an osteoporosis concomitant condition which has not been addressed from the STRIDE study, and will monitor markers of bone turnover during this study. Any reports of bone fracture will be captured as an AESI. Any change in BMD over the course of the study will be assessed using DXA scans where available.

1.4.3 Safety Data Review

The ongoing safety of study subjects will be reviewed by the Medical Monitor and study site physicians as data are received. In addition, safety data will be reviewed in aggregate by the Safety Review Committee (SRC) at pre-defined milestones. See [Section 3.11](#). The safety profile of REN001 to date supports further development in clinical studies subject to appropriate subject selection and safety monitoring.

1.5 Dose Selection Rationale

The dose of 100mg once daily used in this study is the same dose used in the 2 feeder studies for mtDNA-PMM subjects: Study REN001-101 (a UK only study) and the STRIDE study.

To date a total of 163 subjects have been enrolled and 106 subjects received REN001 in four completed clinical trials pertinent to this indication (HPP593-101 (single dose, healthy volunteers); HPP593-102 (14-day, repeat dose study in obese moderately dyslipidemic subjects); HPP593-103, (28-day, healthy volunteer pharmacodynamic study in induced muscle atrophy); REN001-101 (up to 48 weeks, repeat dose in mtDNA-PMM subjects; treatment received for up to 40 weeks due to curtailment of study during the COVID-19 pandemic). In the single dose study, doses ranged from 25mg to 250mg, doses in the 14-day study ranged from 50mg to 200mg QD or 100mg BID, in the 28-day study the dose was 100mg BID and in the 48-week study the dose was 100mg QD. Overall, REN001 was considered safe and well tolerated in all four clinical studies. No treatment related SAEs were reported. No clinically significant abnormalities were observed in any safety parameters including vital signs, ECGs, and physical exams.

In Study REN001-101, most subjects with mtDNA-PMM who received REN001 at an oral dose of 100mg once daily for 12 weeks improved 12MWD, 30 second sit to stand, VO₂ max and gait analysis with these physical function measures being supported by the PRO data. PRO data also reported a reduction in muscle related symptoms and fatigue. Pharmacological activity of the REN001 at 100mg per day was also shown in Phase 1 studies in other indications (see Investigator Brochure for details).

The safety and the pharmacodynamic effects observed in these four completed studies support the 100mg QD dose level in the primary mitochondrial myopathy population evaluated in both the STRIDE study and in this long-term safety study. Although, there is no prior history of REN001 exposure in patients with nDNA mutations, the safety profile of REN001 in this population is not expected to differ significantly from patients with mtDNA mutations. nDNA-PMM patients enrolling in this study must meet similar screening safety

requirements as the naïve mtDNA-PMM patients who previously enrolled in the STRIDE study or in the REN001-101 study.

For completeness, Phase Ib clinical trials have also been completed in Fatty Acid Oxidation Disorder, n= 24 subjects, 50mg or 100mg dose once daily; and McArdle Disease, n= 17 unique subjects, 100mg dose once daily; please see Investigator's Brochure.

2 STUDY OBJECTIVES

2.1 Primary Objective

To evaluate long-term safety and tolerability of REN001 in subjects with PMM.

2.2 Secondary Objectives

To assess subjects with mtDNA-PMM who are receiving long-term treatment with REN001 in terms of PMM associated symptoms, pain severity and interference, exercise endurance, quality of life (QoL), patient global impression of change (PGIC) and patient global impression of severity (PGIS) for muscle and fatigue, and work productivity.

2.3 Pharmacokinetic (PK) Objectives

To further characterise the PK profile of REN001 in subjects with PMM receiving long-term treatment.

2.4 Exploratory Objectives

To evaluate the effect of long-term treatment with REN001 on bone health.

To assess subjects with nDNA-PMM who are receiving long-term treatment with REN001 in terms of PMM associated symptoms, pain severity and interference, exercise endurance, quality of life (QoL), patient global impression of change (PGIC) and patient global impression of severity (PGIS) for muscle and fatigue, and work productivity.

3 OVERALL DESIGN AND PLAN OF THE STUDY

3.1 Overview

This is a long-term safety study for subjects who have completed treatment in the STRIDE study, subjects who participated in the REN001-101 study and nDNA-PMM subjects. At sites with the IEC and regulatory approvals, eligible subjects will be treated for 48 months. A SRC will review safety data during the study. The structure, function, and operation of the SRC is detailed in the REN001-202 SRC Charter. Interim data cuts may be taken, and summaries prepared to support regulatory submissions or external communications such as publications. Subjects with mtDNA mutations enrolling from the STRIDE study will be switching from taking blinded REN001 or placebo in the STRIDE study to open label REN001 in this study. At the time of enrolment into this long-term study, prior treatment allocation in the STRIDE study will be unknown. Subjects who are nearing completion of the STRIDE study will be invited to discuss continuing into this long-term safety study and provide informed consent prior to any study activities. It is expected that most subjects transferring from the STRIDE study will do so at the STRIDE Week 24 visit to prevent an interruption in dosing and reduce the number of study visits and assessments. Subjects who are enrolled at the STRIDE Week 24 visit will not need to complete the STRIDE follow-up (FU) visit.

Alternative exclusion criteria ([Section 4.3](#)) apply to subjects who will be enrolled from sites in Germany. These criteria will require screening blood tests within 8 weeks prior to the start of dosing in this study. For those subjects wishing to start dosing immediately after the STRIDE Week 24 visit, their STRIDE Week 18 blood tests may be used as the screening assessments. However, additional blood samples will need to be collected for HbA1c and serology. See section 6.1.1 for details.

Enrolment at the STRIDE FU visit will require additional baseline assessments. For subjects at the German sites wishing to start dosing in this study immediately after the STRIDE FU, their STRIDE Week 24 blood tests may be used as the screening assessments; additional blood samples will need to be collected for serology. See [Section 6.1.2](#) for details.

Subjects who wish to take part in this study after leaving the STRIDE study (i.e., after their STRIDE FU visit), who participated in Study REN001-101 (UK only), and nDNA-PMM subjects will require additional screening and baseline visits; details of enrolment options are provided in [Section 6.1](#) and [Table 2](#).

The PSOC will assess if nDNA-PMM subjects have the appropriate diagnosis for entry into the study prior to dosing. Subjects who successfully complete screening and are approved by the PSOC will then undergo a Baseline Visit.

After the baseline visit, each subject will have study visits at Months 1, 3, 6, 12, 18, 24, 30, 36, 42 and 48 (and Month 9 and 15 for German subjects). As a final follow-up there will be a telephone call from the study centre to the subject approximately 30 days after the last dose of study drug. A final follow-up telephone call will not be required if mavodelpar has been approved within the country and the subject switches to commercially available medication.

Where the site permits, a concierge service will be available to subjects to arrange hotel accommodation and transport to and from study centre visits and to reimburse any subject study expenses, if applicable. If a study centre requires it, subjects may be asked to have a negative COVID-19 test prior to undertaking scheduled visits at the study centre.

It is expected that most mtDNA-PMM subjects will enrol at the STRIDE Week 24 visit to prevent an interruption in dosing and reduce the number of study assessments. The requirement for screening and baseline visits will be dependent on when the subject enrolls in

the study:

[figure not shown]
- Option 1: Enrolment at the STRIDE Week 24 visit: Most of the STRIDE Week 24 assessments will be regarded as the baseline assessments for this study. Additional assessments will be performed as noted in [Section 6.1.1](#).
- Option 2: Enrolment at the STRIDE FU visit: The STRIDE FU visit will be regarded as the baseline visit for this study with additional assessments performed as noted in [Section 6.1.2](#). If a washout period for any prohibited medication started since the STRIDE Week 24 visit, the subject will exit the STRIDE study and will require additional screening and baseline visits to enter the STRIDE AHEAD Study (Option 3 enroller).
- Option 3: Enrolment after exiting Study REN001-101 or STRIDE (mtDNA-PMM subjects): separate screening and baseline visits will be required, with assessments performed as noted in [Section 6.1.3](#).
- Option 4: Enrolment of nDNA-PMM subjects: separate screening and baseline visits will be required, with assessments performed as noted in [Section 6.1.4](#). nDNA-PMM subjects will not be enrolled in France.

The study design is shown in [Figure 1](#) below. Full details of assessments required for the enrolment options is given below and shown in [Table 2](#).

Figure 1: Study Design

SUBJECT SOURCE:

LONG-TERM SAFETY STUDY

3.2 Endpoints

3.2.1 Primary Endpoints

For mtDNA and nDNA subjects:

- Number and severity of adverse events (AEs)
- Number of AEs leading to study drug discontinuation
- Number of serious adverse events (SAEs)
- Number of adverse events of special interest (AESI)
- Number of AEs leading to death

3.2.2 Secondary Endpoints

For mtDNA and nDNA subjects:

- Absolute values, changes from baseline, and incidence of potentially clinically significant changes in:
 - Laboratory safety tests
 - Electrocardiograms (ECG)
 - Supine vital signs
 - Eye assessments

For mtDNA subjects:

- Absolute values and changes from baseline in:

- Distance walked during the 12MWT*
- MFIS total scores and sub-scale scores*

Patient Global Impression of Severity (PGIS) scores for fatigue and muscle symptoms

- Brief pain inventory (BPI) pain severity and pain interference scores*
 - Patient Reported Outcomes Measurement Information System (PROMIS) Short Form- Functional Assessment of Chronic Illness Therapy (FACIT) Fatigue 13a scores*
 - 36-Item Short Form Health Survey (SF-36) domain scores (7-day recall)*
 - Work Productivity and Activity Impairment Questionnaire: Specific Health Problem (WPAI:SHP) scores*
 - First 6-minute walk distance and last 6-minute walk distance*
 - Phenotypic description questions*
- Patient Global Impression of Change (PGIC) scores for fatigue and muscle symptoms

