3.2.2. Secondary Endpoints

- Absolute values, changes from Baseline and incidence of potentially clinically significant changes in:

- Laboratory safety tests
- Electrocardiograms (ECGs)
- Vital signs
- Eye assessments

For mtDNA-PMM subjects

- Absolute values and changes from Baseline in:
 - Distance walked during the 12-minute walk test (12MWT)*
 - Modified Fatigue Impact Scale (MFIS) Total scores and sub-scale scores*
 - Patient Global Impression of Severity (PGIS) score for fatigue and muscle symptoms
 - Brief Pain Inventory (BPI) pain severity and pain interference scores*
 - Patient-Reported Outcomes Measurement Information System (PROMIS) Short Form – Functional Assessment of Chronic Illness Therapy (FACIT) Fatigue 13a scores*
 - 36 Item Short Form Survey (SF-36) domain scores (7-day recall)*
 - Work Productivity and Activity Impairment questionnaire: Specific Health Problem (WPAI:SHP) scores*
 - First 6-minute walk distance and last 6-minute walk distance*
 - Phenotypic description questions
- Patient Global Impression of Change (PGIC) scores (muscle and fatigue symptoms)

**Collected up to Month 24 only.*

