6. SAFETY ASSESSMENTS

The primary purpose of this study is to assess the long-term safety and tolerability of dosing with mavodelpar 100 mg once daily. The sections below detail the safety assessments, including any derivations required. The analyses of the safety endpoints are detailed in [Section 10](#).

Details concerning the baseline used in the derivation of changes from baseline are provided in [Section 8.6](#).

Subjects attending sites in Germany will have additional safety assessments at Month 9 and Month 15. These safety assessments include ECGs, vital signs, safety laboratory evaluation and physical examinations. The data from these assessments will not be included in any ‘by visit’ summaries but will be listed and will be considered in summaries of results of potential clinical importance.

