6.4. VITAL SIGNS

Changes from baseline will be calculated for each vital sign parameter (systolic and diastolic blood pressure, pulse, weight and temperature) for each scheduled visit. Change

from baseline for systolic and diastolic blood pressure will be calculated irrespective of whether the arm used for the blood pressure assessment is the same at both visits.

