12.4. VITAL SIGNS

Observed and change from baseline values will be summarized by visit using descriptive statistics.

Box plots of change from baseline by visit and group will be presented for measurements. The whiskers will display the 5th and 95th percentiles and outliers will be identified on the plot with subject ID. The number of observations contributing to each visit box plot will be included.

The number and percentage of subjects with an increase or decrease from baseline in systolic blood pressure of <10 mmHg, ≥ 10 to <20mmHg, ≥ 20 to <30 mmHg or ≥ 30 mmHg will be summarized by visit. The denominator for percentages will be the number of subjects still on-treatment. This summary will be repeated for diastolic blood pressure using the following categories <5 mmHg, ≥ 5 to <10 mmHg, ≥ 10 to <15 mmHg, ≥ 15 to <20 mmHg, ≥ 20 to <25 mmHg or ≥ 25 mmHg.

Observed and change from baseline values will be listed. The listing will identify the increase or decrease from baseline categories detailed above for systolic and diastolic blood pressure.

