12.5. ECG

Observed and change from baseline values will be summarized by visit using descriptive statistics.

A shift table from baseline to visit, for overall ECG interpretation (normal, abnormal not clinically significant, abnormal clinically significant and missing) will be summarised with marginal totals, using counts and percentages.

A shift table from baseline to the maximum post baseline QTcF value will be summarized according to the categories specified in the table below. The maximum will be taken from all scheduled and unscheduled on-treatment values.

Parameter	Criteria
QTcF	
< 450 msec
 
≥ 450 msec and < 480 msec*
 
≥ 480 msec and < 500 msec*
 
≥ 500 msec*

QTcF increase from baseline	
< 30 msec
 
≥ 30 msec and < 60 msec*
 
≥ 60 msec*

* Values of PCI.

Observed and change from baseline values will be listed. The listing will identify QTcF values of PCI (identified in the above table).

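### Vital signs fall under an incidence endpoint, but no SAP table counts subjects who ever had a large change on treatment, and the German Month 9 and 15 readings are routed to a summary that does not exist

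*Protocol*

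**What the plan says.** **Endpoint.** Protocol Section 3.2.2 lists, for mtDNA and nDNA subjects, "Absolute values, changes from baseline, and incidence of potentially clinically significant changes in" laboratory tests, ECGs, supine vital signs and eye assessments. SAP Section 3.2.2 carries this over as "Absolute values, changes from Baseline and incidence of potentially clinically significant changes in" the same four items.

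**Protocol analysis text.** Protocol Section 8.6 has vital signs summarised by visit and mentions incidence of potentially clinically significant values only for laboratory and ECG data.

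**Vital signs in the SAP.** SAP Section 6.4 names the parameters as "systolic and diastolic blood pressure, pulse, weight and temperature". For these, Section 12.4 states: "Observed and change from baseline values will be summarized by visit using descriptive statistics". It adds box plots of change by visit and group. The only categorical table begins "The number and percentage of subjects with an increase or decrease from baseline in systolic blood pressure", has four bands with the top one at 30 mmHg or more, and is made visit by visit among subjects still on treatment. Diastolic pressure follows: "This summary will be repeated for diastolic blood pressure using the following categories", with six bands up to 25 mmHg or more. The listing flags the bands for both pressures.

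**Other items under the same endpoint.** SAP Section 12.2 counts subjects with one or more on-treatment post-baseline values, unscheduled ones included, that meet a stated criterion for CK, aldolase, troponin I or potential Hy's Law. For QTcF, Section 12.5 says: "The maximum will be taken from all scheduled and unscheduled on-treatment values".

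**German visits.** SAP Section 6 keeps Month 9 and Month 15 assessments, vital signs among them, out of by-visit summaries. It says instead that they "will be listed and will be considered in summaries of results of potential clinical importance".

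**Changes from protocol.** SAP Section 14 declares none.

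**The concern.** An incidence endpoint asks how many subjects had the event. The planned table answers a narrower question: how many subjects were in a given band at a given visit. A subject with one large rise at Month 18 appears in the Month 18 row and nowhere else, and a subject with a large rise at every visit appears in every row. The rows therefore cannot be added, and none of them gives the number ever affected over 48 months. Neither document says which change in a vital sign counts as potentially clinically significant.

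The German rule is a separate gap and does not depend on how incidence is read. The two extra visits were added at a regulatory agency's request (Protocol synopsis), and vital signs are taken at both (Protocol Sections 6.5 and 6.7). The SAP excludes these readings from one kind of table and assigns them to another kind that Section 12.4 does not contain. Followed as written, the plan leaves them in listings only.

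At stake is one component of a descriptive secondary safety endpoint, in a study whose primary objective is long-term safety. No test, error rate or sample size is affected.

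**Working it through.** The plan states no figure for this endpoint, so there is none to reproduce. The check compares the sections, then asks what by-visit counts can say about any-time incidence.

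**1. What each measurement gets**

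| Measurement | By-visit statistics | Change bands by visit | Per-subject any-time or worst-value count |
|---|---|---|---|
| Selected laboratory parameters (SAP 12.2) | yes | not applicable | yes, unscheduled included |
| QTcF (SAP 12.5) | yes | not applicable | yes, unscheduled included |
| Systolic and diastolic pressure (SAP 12.4) | yes | yes | no |
| Pulse, temperature, weight (SAP 12.4) | yes | no | no |

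Of the five parameters in SAP 6.4, two have a categorical table and none has a per-subject count over the treatment period.

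**2. Readings that reach a table**

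- *German subjects:* 12 post-baseline visits, of which 2 (Month 9 and Month 15) enter no vital-sign summary.
- *Unscheduled readings:* under SAP 8.4 a scheduled on-treatment reading in a window takes precedence over any unscheduled one there, and data outside the windows are only listed. An unscheduled reading therefore counts only if it falls in a window with no scheduled on-treatment reading.
- *Share of time covered:* the REN001-202 windows that feed by-visit tables, up to Day 1344, are Month 1 (15 days), Months 3 and 6 (43 each), Months 12, 18, 24, 30, 36 and 42 (85 each), and Month 48 (Days 1302 to 1344, 43 days). The sum is 15 + 43 + 43 + 6 × 85 + 43 = 654 of the 1,343 days from Day 2 to Day 1344, or 48.7%. On the other 51.3% of days an unscheduled reading cannot enter a by-visit count.

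**3. From by-visit counts to any-time incidence**

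Let n_v be the number of subjects in the band at visit v. With no dropout and N subjects, the number ever in the band satisfies

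max(n_v) ≤ number ever ≤ min(N, sum of n_v).

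The lower limit is reached if the same subjects recur at every visit, the upper if each visit's subjects are new. For a constant per-visit proportion p over 10 visits, any-time incidence lies between p and min(1, 10p). Independence between visits gives 1 − (1 − p)^10, which is inside that range and is not its ceiling.

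The documents give no vital-sign event rate, so p is an assumption:

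| Assumed p | Range of any-time incidence | If visits were independent |
|---|---|---|
| 1% | 1% to 10% | 9.6% |
| 2% | 2% to 20% | 18.3% |
| 5% | 5% to 50% | 40.1% |

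Take 200 subjects (about 150 mtDNA plus up to 50 nDNA, SAP 3.5). At p = 2% each visit row shows 200 × 0.02 = 4 subjects. The number ever affected could be anything from 4 to 10 × 4 = 40. The same by-visit table fits every value in that range.

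**The case against.** Much of the opposing case stands.

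- **The mismatch starts in the protocol.** Section 8.6 plans by-visit summaries for vital signs and names incidence for laboratory and ECG data only. SAP 12.4 does what Section 8.6 asks and adds the blood-pressure bands. That explains the gap, but both documents still list vital signs under the incidence endpoint, and SAP Section 14 records no change.
- **The endpoint is partly served.** A reader might infer that it has no valid estimate at all. The documents do not support that. Absolute values and changes are summarised, and the pressure bands give a visit-specific frequency. Neither document says that incidence must be cumulative.
- **Only the bands are limited to blood pressure.** A reader might infer that pulse and temperature are not summarised. They are, in the by-visit statistics and box plots.
- **Selecting parameters is usual in this SAP.** Sections 12.2 and 12.5 also cover only some laboratory and ECG parameters. The absence of bands for every vital sign is therefore not by itself an anomaly. Weight, moreover, is part of physical examination in Protocol Section 7.1.3 and is not among the supine vital signs of Section 7.1.4.
- **Nothing is lost.** The readings are listed with bands flagged for both pressures, and the Safety Review Committee sees vital signs (Protocol Section 3.11). A listing is still not a count.
- **The true spread may be narrower than the illustration.** All of a subject's changes share one baseline, so visits are correlated. Dropout and the unknown number of German subjects also matter.

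None of this supplies the missing count or gives the German readings a destination.

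**Conclusion.** The point holds in a limited form. The incidence part of the vital-sign endpoint has no criterion for potential clinical importance and no any-time count per subject, whereas the SAP provides both for selected laboratory parameters and QTcF. The routing rule in SAP Section 6 has nowhere to send the German Month 9 and Month 15 vital signs.

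The text alone establishes both gaps. Their numerical size cannot be established from the documents. The range from p to 10p rests on an assumed constant rate, 10 visits and no dropout, and shows only that by-visit counts leave any-time incidence undetermined. It does not predict how many subjects will be affected. The top pressure band should not be read as the definition of potentially clinically significant, because neither document says so.

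This is worth correcting before database lock. It does not threaten the primary safety endpoints, which rest on adverse events.

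**What to change.** 1. Add to SAP Section 12.4 a per-subject table of the largest increase and the largest decrease from baseline in systolic and in diastolic pressure. Take these over all on-treatment post-baseline readings: scheduled, unscheduled, and German Month 9 and Month 15. Use the bands already defined. The denominator is subjects with a baseline and at least one on-treatment post-baseline reading.
2. State before database lock which bands count as of potential clinical importance. The clinical team sets these thresholds. The table then becomes the destination that SAP Section 6 assumes.
3. Treat pulse in the same way, with bands set by the clinical team, or record in SAP Section 14 that incidence is reported for blood pressure only. If pulse is added, the Section 14 note should still say how temperature is handled.

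The cost is some SAP wording and one extra table per presentation. The data are already collected. Because an any-time count rises with time on treatment, it should be read beside the exposure summary in SAP Section 9.5.
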